Acceptance of FACE among African-American families has been high. 6,9,56 Among African-Americans living with HIV (n=192), 91% in the FACE intervention completed an advance directive, while only 15% in the control had completed an advance directive. 107 Study findings may increase equity in pACP, recognized by the Centers for Disease Control as minimizing suffering, 104 and improving public health. 108 Study outcomes are related to the National Consensus Project domains for palliative care: 109 psychological (emotional health, caregiver strain, caregiver distress), social (positive caregiving appraisals, family well-being), and spiritual (meaning/peace) and attend to the cultural and ethical domains of care. 110-113 There is an ethical imperative to engage in pACP, ¹¹⁴ despite the real concerns about the emotional impact, ^{56,115-117} because these conversations may actually support hope. 118-122 A.2.b. Development, Feasibility & Beta Testing of Integrated 4-session FACE-Rare. Our team developed and beta-tested the integrated FACE-Rare intervention at Children's National. 41 Of 9 families approached, 8 enrolled and 7 completed baseline. All 7 children had total parenteral nutrition (TPN) and 5 were wheelchair bound. All family caregivers were mothers and 43% African-American. Of the 6 mothers who began Session 1, 100% completed all 4 sessions and the 2week follow-up assessment. The most frequently rated support need for their child, "Knowing what to expect in the future when caring for my child." Satisfaction ratings demonstrate 100% reported the sessions were useful and helpful, while half felt sad talking about goals of care. Two African-American fathers participated in creating advance care plans. This is significant as male caregivers are rarely studied. 123 They have agreed to participate in the Community Advisory Board to increase male caregiver participation in FACE-Rare. See Letters of Support. Average time to complete questionnaires was 27 minutes and families reported no respondent burden. 124 Findings demonstrate feasibility and acceptability. Families who participated in the development and beta-testing will not be eligible to participate in this R21. Parents reported, "Dealing with perpetual grief" and "Living on the precipice." Overall impact is high because findings will improve scientific knowledge of clinical practice supporting family caregivers whose children experience high rates of mortality 125 change to Specific Aims number and may decrease family caregiver strain, associated with higher overall mortality for family caregivers of older adults. 125

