AIM 1. To evaluate the initial efficacy of FACE-Rare in a pilot RCT on primary outcome: family QoL at 3-months post-intervention to seek effect sizes for a future fully powered R01. Hypotheses (H) 1a: FACE-Rare families will report significantly better QoL (emotional, spiritual) compared to controls. We will first describe the level of the outcome measures at both baseline and 3-month post-intervention by intervention group. Each group's preand post-intervention outcome levels at will be compared using paired t-test, respectively. Difference in change of each QoL measure from T₁ to T₂ between intervention groups will be examined using t-test. We will then apply the reliable change index (RCI)^{152,153} to assess how many individual patients in each intervention group would make a clinically significant amount of improvement in each of the QoL measures based on their RCI scores. The bias in outcome changes caused by measurement errors in the QoL scores will be taken into account in RCI. We will provide graphic portraval of individual outcome changes and RCIs by intervention group. An RCI of ±1.96 will serve as criteria for classifying the patients into categories of improved, unimproved, and deteriorated based on their QoL scores and RCIs. Those categories will be compared by intervention groups using two-sided Fisher's exact test. Based on our previous studies, we will assume a reliability of 0.80 for each of the QoL measure for conducting RCI. Because the focus on the individual rather than the group as a whole, data provided by the RCI allows the identification of individuals whose QoL measures have only changed marginally, or in an unusual direction, allowing the identification of subgroups for further analysis. The RCI thus also provides a systematic screening tool that has some advantages over the traditional visual inspection or setting cut-off points for inclusion based only on change relative to the group.

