- 2. If something did upset a participant, after supporting the family, the RA will ask if there is a staff person they feel comfortable with that they would like to meet with and we will contact that staff person to support the participant.

Families of children who are in the Intensive Care Unit (ICU) are very ill and will not be "bothered" by activities unrelated to their crisis. Therefore, families of children who are in the ICU will not be approached for enrollment. If a child later is discharged from the ICU, the family can be enrolled. If at some point during the study a family who has started the intervention has a child who becomes admitted to the ICU and this ICU admission occurs during a planned study visit, research staff will ask the treating physician if they feel it is appropriate to approach the parents/legal guardians about completing the study visit or reschedule based upon the severity of the admission. The treating physician, health care provider and parents/legal guardians' wishes will be respected. Each study site has a system in place to notify research staff of the death of a patient within 24 hours. This will prevent the risk that a family will be contacted about a study visit by the RA who does not know that the patient died.

Adverse Events (AE): We have operationalized the definition of a Serious Adverse Event (SAE) and Adverse Event using the PI developed Satisfaction Questionnaire, which we used in previous research of advance care planning with adolescents with HIV and cancer. To date our research has demonstrated no serious adverse event or adverse event, even though the process is emotionally intense. These definitions were approved by our *IRB* and our Safety Monitoring Committee (SMC) for our previous studies, as the IRB thought we had too low a bar for an adverse event.

Monitoring will occur on a daily basis to review any SAs or SAEs. RAs have the PIs cell phone number and are encouraged to call directly with any concerns. [name] is on call for [name] whenever [name] might not be reachable by cell. The REDCap data base has an alert built into the program if responses to the Satisfaction Questionnaire meet the criteria for an adverse event. These items were derived from community based participatory research. Participants sometimes report FACE pACP is hurtful and worthwhile, for example.⁵⁵

Operationally Defined Adverse Event:

Careful Ongoing Monitoring for Adverse Events

Form	Name	Item	Question	Answer

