16	Satisfaction Questionnaire	5	It was too much to handle	Agree/Strongly Agree
16	Satisfaction Questionnaire	7	It was harmful	Agree/Strongly Agree
Form	Name	Item	Question	Answer
16	Satisfaction Questionnaire	1	It was useful	Disagree/Strongly Disagree
16	Satisfaction Questionnaire	2	It was helpful	Disagree/Strongly Disagree
16	Satisfaction Questionnaire	6	I felt satisfied	Disagree/Strongly Disagree
16	Satisfaction Questionnaire	11	I felt courageous	Disagree/Strongly Disagree
16	Satisfaction Questionnaire	13	It was worthwhile	Disagree/Strongly Disagree

For the purposes of this study an adverse event is when ONE of the following statements are endorsed on the . **Agree or strongly agree:**

- o "It was too much to handle." OR
- "It was harmful."
 AND

In addition to one of the above statements being endorsed, ALL of the following must be endorsed for an adverse event to occur. **Disagree or Strongly Disagree**

- "It was useful."
- "It was helpful."
- o "I felt satisfied."
- "I felt courageous
- "It was worthwhile."

Definition of Serious Adverse Events (SAEs)

For the purposes of this study a serious adverse event will be defined as an emotional breakdown requiring hospitalization or inpatient behavioral health services for emotional distress very likely/certainly related to the study intervention.

Any serious adverse event occurring during the protocol conduct will be reported and reviewed by the PI, [name]. Any serious adverse event will be monitored to ensure the event was actually caused by the intervention, and not some coincidental issue. These events will be collected and reported in compliance with the local IRB guidelines. The PI and *IRB* must be notified within 24 hours of the reported serious adverse event. We will discontinue the study until a corrective action plan is in place.

The PI and *IRB* must be notified not more than 5 days after becoming aware of an adverse event. Training will continue throughout the course of the study to minimize the likelihood of such an SAE.

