1. Screening. Following the consent/assent process, guardians/family caregivers will complete a brief screener. Participants will be informed that should the screening reveal any evidence of a significant mental health issue, they will be referred to a mental health professional at the clinic/hospital or in the community for further assessment.

Immediately following completion of all screening questionnaires, the RA-Assessor will review the potential participant's responses to identify active psychosis or homicidality or suicidality (assessed by interview using structured questions. Family caregiver endorsement of current suicidality, homicidality, or active psychosis will activate the following procedures:

- The research assistant (RA) will contact the PI to help determine if there is a clear or immediate danger. The PI is experienced in these kinds of assessments for dangerousness, or:
- If the RA cannot reach the PI, the RA will contact/page the psychiatrist/social worker on call, who will either come to the research office to assess whether or not there is a clear and immediate danger to self or others or conduct the assessment at the emergency department;
- If the on call psychiatrist cannot be reached, the RA will escort the participant to the emergency department;
- In each instance, the RA will remain with the participant until the appropriate health care provider takes responsibility for the assessment and care of the participant.
- 2. CSNAT. If a family member is overwhelmed by strong feelings during the CSNAT interview, we will follow the procedures below in #3.
- 3. Intervention. Although we had no adverse events during our FACE trial, we appreciate that despite the structure of the pACP intervention, which was designed to contain strong emotions in a

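### A zero under the questionnaire adverse-event rule cannot show that no caregiver reported harm, because a single benefit item left unrejected removes the harm answer from the count

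*Combined protocol and SAP*

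**What the plan says.** The rule is built on the Satisfaction Questionnaire. The first condition is agreement or strong agreement with item 5 (too much to handle) or item 7 (harmful). The second is joined to it by AND: "In addition to one of the above statements being endorsed, ALL of the following must be endorsed for an adverse event to occur". The listed items are 1 (useful), 2 (helpful), 6 (satisfied), 11 (courageous) and 13 (worthwhile), each to be answered disagree or strongly disagree. The table and the text of that section agree.

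The Adverse Events (AE) paragraphs just before it add three things:

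- The database has an "alert built into the program if responses to the Satisfaction Questionnaire meet the criteria for an adverse event".
- The definitions were approved by the IRB and the Safety Monitoring Committee for previous studies, "as the IRB thought we had too low a bar for an adverse event".
- "Participants sometimes report FACE pACP is hurtful and worthwhile, for example".

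An adverse event must reach the PI and the IRB within 5 days, and the Committee reviews all of them. Serious adverse events are defined separately and require hospitalization or inpatient behavioral care.

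Earlier zero counts are cited as reassurance. The Adverse Events section says: "To date our research has demonstrated no serious adverse event or adverse event, even though the process is emotionally intense". Families in emotional distress, point 3, opens: "Although we had no adverse events during our FACE trial". Resolving Disagreements says much the same of the preliminary studies.

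On analysis, Aim 2 in D.9 compares satisfaction between arms with the H1a methods. It states no tabulation of items 5 and 7.

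**The concern.** A reader of the final report will naturally take zero adverse events to mean that no caregiver found the sessions harmful or overwhelming. Under this rule it cannot mean that. It means only that no caregiver both gave a harm answer and denied all five benefits. Two quite different outcomes produce the same zero: nobody reported harm, or some did but also saw value in the sessions. The protocol's own remark about mixed reports makes the second outcome a practical possibility.

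The stake is what this pilot can say about safety when it is used to support an R01. It also affects what reaches oversight by default, because the alert, the 5-day notice and the Committee's review of adverse events all depend on the composite. The Committee chooses its own data summaries, so it may or may not ask for the two harm items.

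**Working it through.** The documents attach no rate, power or sample-size figure to this rule, so there is nothing to reproduce. The check is logical, followed by one exact bound.

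**Inputs.** The rule, from Operationally Defined Adverse Event. 15 dyads in the FACE-Rare arm, from Human Subjects Involvement. Beta-test ratings, from A.2.b.

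**Step 1: the rule as a formula.**

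AE = (item 5 agreed OR item 7 agreed) AND (items 1, 2, 6, 11 and 13 all rejected)

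Hence the AE count cannot exceed the number of caregivers who reject the least-rejected benefit item. If every caregiver agrees with any one of the five, the count is 0 whatever was answered on items 5 and 7.

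**Step 2: how narrow the rule is.** Reduce each of the seven items to two answers:

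- All patterns: 2^7 = 128.
- Patterns with a harm answer: 3 of the 4 combinations on items 5 and 7, times 2^5 = 32 combinations on the rest, so 3 × 32 = 96.
- Patterns that count as an adverse event: 3 × 1 = 3.
- Harm patterns not counted: 96 − 3 = 93.

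This counts answer patterns. It does not estimate how often they occur.

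**Step 3: what a zero says about FACE-Rare.** If all 15 caregivers agree with at least one benefit item, zero adverse events fits any number of harm answers from 0 to 15. It therefore sets no upper bound on the harm-answer rate; it bounds only the composite.

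**Step 4: what a direct count would say.** The one-sided exact 95% upper bound after 0 of n is 1 − 0.05^(1/n). For n = 15, with every form returned, 1 − 0.05^(1/15) = 0.181, or about 18%. Fewer returned forms would give a wider bound.

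**Step 5: illustration under assumed rates.** Let p be the share endorsing item 5 or 7, and q the share of those who also reject all five benefit items. Neither is in the documents. With independent caregivers,

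P(at least one harm answer and zero AEs) = (1 − pq)^n − (1 − p)^n.

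For n = 15:

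| p | q = 0.05 | q = 0.10 | q = 0.25 | q = 0.50 |
|---|---|---|---|---|
| 0.1 | 0.722 | 0.654 | 0.478 | 0.257 |
| 0.2 | 0.825 | 0.703 | 0.428 | 0.171 |

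For p between 0 and 1, the probability is zero only if q = 1, meaning that nobody who reports harm sees any benefit. The spread from 0.171 to 0.825 shows why no single figure should be quoted.

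**The case against.** **The threshold was chosen and approved.** True. The section says so for previous studies, and serious events have their own definition. This explains the rule but does not change what a zero under it means.

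**Harm answers are not lost.** Largely true. The answers are collected, and staff administer the measures, read questionnaires to caregivers, support anyone distressed and are encouraged to call the PI with concerns. Session 3 recordings, where consented, are reviewed for safety. The role-stress scale is taken at baseline and 3 months, and the reliable change analysis involves "classifying the patients into categories of improved, unimproved, and deteriorated based on their QoL scores and RCIs". A reader might infer that the trial disregards caregivers who say they were harmed. The documents do not support that: the gap is in the adverse-event label, its alert and the stated reporting. None of these other routes, however, is stated to count caregivers who gave either harm answer.

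**The plan never equates zero adverse events with no reported harm.** Also fair. The zeros cited concern earlier research, and the plan openly calls the process emotionally intense. No stated hypothesis or progression rule uses the count. The statements still serve as reassurance, and the same rule will produce this trial's figure.

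**A separate count may exist elsewhere.** This stands. Safety monitoring is referred to a Data Safety and Monitoring Plan and questionnaire details to a Project Narrative, neither of which is in the text provided. The team also reports single items in A.2.b: "Satisfaction ratings demonstrate 100% reported the sessions were useful and helpful, while half felt sad talking about goals of care". The claim is therefore limited to what the available text states.

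**The beta test.** A reader might infer from those ratings that the beta-test count was zero by construction. That follows only if the same questionnaire items were used, which A.2.b does not say. It would also rest on the 6 mothers who completed a 4-session version.

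**Conclusion.** The point holds as a matter of logic and needs no assumed rate. Under the rule as written, zero adverse events cannot show that no caregiver reported harm, and the text provided states no separate count of items 5 and 7. The number of harm answers that would be missed cannot be estimated. The measurable gain from counting them directly is that 0 of 15 FACE-Rare caregivers would support an upper bound of about 18%, assuming complete response; the composite alone supports none.

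This is a limit on what the pilot can claim and on what oversight sees by default. It does not show that the threshold is wrong, that harm occurred, or that distress goes unmanaged. It is worth correcting because the correction is cheap.

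A reader might also infer from the numbering that the rule cannot be met, since it uses item 13 while Table 2 in D.6.b gives the questionnaire 12 items. This is more likely a numbering slip, because the rule is also written out by statement, and the conclusion does not depend on it.

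**What to change.** 1. Keep the approved adverse-event definition unchanged.
2. Add one descriptive table of agree or strongly agree answers to items 5 and 7, each alone and either one, with the number of forms returned. Give it for FACE-Rare, and for controls where they complete the form, at each visit at which it is given. Send it to the Safety Monitoring Committee and include it in the final report. If the Data Safety and Monitoring Plan already provides this, cite it in the analytic plan.
3. Word any safety conclusion so that zero adverse events refers to the composite only, and report the two harm items beside it.

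Peripheral clean-up while editing: reconcile item 13 with the 12 items in Table 2 and check the alert against the fielded form. Also reconcile Visit 4 in Table 2 with the satisfaction assessments at Visits 2, 3 and 4 in D.6, and state when controls complete the form, unless the visit figure (not shown in the text provided) settles this.

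The cost is one table from data already collected, a check of the alert and some wording, with no extra form for families. The downside is a few mixed responses to review, from caregivers who also saw a benefit.

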Therefore, the objectives of the proposed study are (1) to close a gap in our knowledge⁴⁰ by assessing families' needs for support in a heterogeneous group of children with serious, advanced, ultra-rare diseases with and without comorbidities, who are unable to participate in shared medical decision-making; and (2) to test one such pACP intervention which may empower families by providing some control in a low control situation and increase families' capacity to participate in EOL decision making. The FAmily CEntered (FACE) pACP intervention, proven successful with cancer and HIV,⁵⁻¹² is adapted to children with ultra-rare diseases. Theoretically⁴¹⁻⁴⁴ informed and developed by the PI, **[name]**^{5,7} and Consultant, **[name]**,^{5,7} the proposed intervention will incorporate Respecting Choices Next Steps Pediatric ACP™ (RC), developed by [name] (unpublished) and Hammes. 45 specifically tailored for families whose child is unable to participate in health care decision-making. Our consultation with families of children with rare diseases and the National Organization for Rare Disorders (NORD) revealed that basic pPCEOL needs should be addressed first, prior to a pACP intervention. For the study to be able to meet families where they are, prior to randomization, all families will complete the Carer Support Needs Assessment Tool (CSNAT), ©46-51 adapted for use in pediatrics in our preliminary research through collaboration with NORD and affected families. In The CSNAT Approach, facilitators assess the prioritized pPCEOL needs and developed Shared Actions Plans for decision-making support. We propose pilot testing the three weekly sessions of FACE-Rare: CSNAT plus Respecting Choices, using a rigorous intent-to-treat, single-blinded, randomized controlled trial (RCT) design with 30 family/child dyads with 3-month post-intervention assessments. We will accomplish the objectives of this application by addressing the following specific aims:

AIM 1. To evaluate the initial efficacy of FACE-Rare in a pilot RCT on primary outcome: family quality of life (QoL) at 3-months post-intervention, controlling for co-variates (age, sex/gender, race of family caregiver) to seek an effect size for a future R01.

Hypotheses (H) 1a: FACE-Rare families will report significantly better QoL (emotional, spiritual) compared to controls.

H1b: Family caregiving appraisals will moderate effect of FACE-Rare on QoL outcomes.

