As with our previous studies, we will send study results for primary outcomes to study participants in the form of a newsletter. For those patients who may die while on study, the newsletter will be accompanied by a personal letter expressing sorrow for the loss of their child and appreciation for their participation and contribution to the science of pACP. This letter will be personalized and signed by the research staff known to the patient and family.

The risks of participation in this minimal risk study are reasonable in relation to the importance of the knowledge that may result from the study.

Study participants who were randomized to the control condition will be offered the intervention while the study is in the dissemination stage, if study aims are realized. The Co-ls at Children's National are committed to this, as a study service.

Safety Monitoring Committee (SMC)

This study will be conducted in accordance with appropriate sections of the International Conference on Harmonization's Guidelines for Good Clinical Practice (GCP). The principal investigator, [name], will be responsible for monitoring and the process by which adverse events and unanticipated problems will be reported to all relevant regulatory bodies. See **Data Safety and Monitoring Plan** for more details.

[name] will compile a Safety Monitoring Committee (SMC), following the guidelines provided by NINR/NIH. [name] will invite an expert in the full range of issues associated with children with serious illnesses and their families, with additional expertise in evidence-based assessment and intervention, specific to the goals of this Program Announcement to identify and meet the palliative care needs of persons with rare diseases and their families. Three additional members will be invited who are experts on quality of life measurement, data safety, and the science and ethics of research on palliative care for children.

The SMC will meet a minimum of once a year. The SMC will decide what data summaries it wants to see in order to adequately monitor the data and the safety of the patients and families in the study.

The SMC will review all adverse events, for immediate assessment of any safety concerns in the study. All serious adverse events will be reported to the PI, SMC and the IRB within 24 hours of event knowledge. [name] will then notify the Research Nurse Coordinator, [name], who will coordinate notifications.

References

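### Relatedness is built into the SAE definition, so a control caregiver cannot have an SAE during randomized follow-up and a possibly related distress hospitalization is not in itself an SAE or an AE

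*Combined protocol and SAP*

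**What the plan says.** The rules are in the human subjects section, under Protection Against Risks, with a further paragraph under Safety Monitoring Committee (SMC).

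- **SAE.** The definition is "emotional breakdown requiring hospitalization or inpatient behavioral health services for emotional distress very likely/certainly related to the study intervention". Shortly after it comes: "Any serious adverse event will be monitored to ensure the event was actually caused by the intervention, and not some coincidental issue". The PI and IRB are to be told within 24 hours of the reported SAE, and then: "We will discontinue the study until a corrective action plan is in place".
- **AE.** The rule opens "For the purposes of this study an adverse event is when ONE of the following statements are endorsed on the" (the instrument's name is missing there, but the table above it identifies the Satisfaction Questionnaire). The two statements are that participation was too much to handle or was harmful. It continues: "In addition to one of the above statements being endorsed, ALL of the following must be endorsed for an adverse event to occur". The further items are disagreement with five positive statements.
- **Source of both.** The AE paragraph says "We have operationalized the definition of a Serious Adverse Event (SAE) and Adverse Event using the PI developed Satisfaction Questionnaire", although the SAE definition uses no questionnaire item.
- **SMC section.** "All serious adverse events will be reported to the PI, SMC and the IRB within 24 hours of event knowledge". The SMC is on this 24-hour list but not on the one in the SAE definition.
- **Exposure of controls.** Section D.6 offers control families the intervention only once their own participation has ended.

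**The concern.** Seriousness and causality are normally recorded separately: an event is captured because of what happened, and its cause is graded afterwards. Here the cause decides whether the event exists in the safety record at all. Distress heads the protocol's own list of potential risks, and the text says these families may be especially prone to it. A pilot meant to lead to a larger R01 will be read for safety as well as for effect size.

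Under this rule a report of no SAEs could mean that no caregiver was hospitalized for distress. It could equally mean that some were and none was attributed strongly enough. The reader could not tell which. The PI reviews SAEs, and the Specific Aims describe the intervention as "informed and developed by the PI" together with a consultant, which is a further reason to keep the grading separate from the capture.

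**Working it through.** The documents give no safety rate, safety hypothesis or caregiver hospitalization risk, so there is no figure to reproduce. The check is to apply the written definitions to cases.

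**Inputs.** 15 dyads per arm (human subjects section 1a). Controls have no intervention sessions during follow-up (D.6). SAE and AE definitions as above. Satisfaction assessments at Study Visits 2, 3 and 4 (D.6), or at Visit 4 only (Table 2), with none listed at 3 months.

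| Caregiver hospitalized for distress during randomized follow-up | SAE? | AE because of the hospitalization? |
|---|---|---|
| TAU | No: there is no intervention to be related to | No |
| FACE-Rare, judged possibly or probably related | No: below the required attribution | No |
| FACE-Rare, attribution at the required level | Yes | No |

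**Step 1, controls.** Row 1 holds for all 15 control dyads, so the control SAE count is 0 of 15 by construction. Controls can still have an AE: H2 compares satisfaction between arms, so they must complete the questionnaire.

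**Step 2, the middle row.** A hospitalized caregiver is an AE only if that person separately gives the questionnaire pattern, that is, at least one of two negative items plus disagreement with all five positive ones. Hospitalization is not among the items. After Visit 4 no further questionnaire is scheduled, so a later hospitalization has no planned form on which even that could happen.

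**Step 3, other collection.** Chart abstraction concerns the child, not the caregiver. The distress procedures at the 3-month assessment lead to support, referral or emergency evaluation; they do not ask for or record past admissions.

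**Step 4, order of judgement.** Set the SAE definition beside the sentence that follows it. If only attributed events are SAEs, a later check that the intervention caused them has nothing left to do. If the check is real, events must first be logged without settled attribution, and the relatedness clause is then not a condition of entry. The clocks differ too: the SAE definition counts 24 hours from the reported SAE, the SMC section from knowledge of the event. The text does not settle whether relatedness comes before or after the report.

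**Step 5, alternative parsing.** The relatedness clause could be attached only to inpatient behavioral health care, leaving hospitalization free of it. The causality check applies to any SAE, which makes that reading less likely.

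**The case against.** A reader might infer that no reporting route exists and that the SMC never sees these events. The documents do not support that. Section D.8.d gives the external SMC a remit over safety and study data generally, and the SMC section lets it choose the summaries it receives. The PI is also responsible for reporting unanticipated problems, and a Data Safety and Monitoring Plan and local IRB guidelines are cited. Any of these may cover the gap, but the plan's content is not available here and unanticipated problems are not defined. The IRB-guideline sentence refers to SAEs as already defined, and the SMC can only request summaries of what someone has recorded.

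A reader might also infer that the PI alone filters events before any report. That is one reading. The later causality check and the event-knowledge clock point the other way, and D.8.d has the SMC review any SAE or AE. What stands is that the order is unclear.

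Four further points are fair. The 3-month screening for suicidality, homicidality and psychosis applies to both arms, although it detects current danger and not past admissions. Section D.9 plans no comparison of SAEs between arms, and 15 per arm would be uninformative for rates under any definition, so the loss is to description and not to a planned test. The definitions were deliberate and had IRB and SMC approval, but for earlier studies; that explains them without removing the consequence. Finally, it is tempting to size the loss by assuming a background hospitalization risk. The documents give none, so any such figure would only restate the assumption.

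**Conclusion.** The point holds. During randomized follow-up a TAU caregiver cannot have an SAE, and a FACE-Rare hospitalization judged only possibly or probably related is neither an SAE nor, in itself, an AE. The available text states no explicit route for recording or reporting it. The SAE text is also inconsistent with itself on when causality is judged, and the two 24-hour rules differ in recipients and starting point.

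The only size the documents support is the structural one: 0 of 15 in the control arm regardless of what happens. How many events would be missed in either arm cannot be stated. A zero SAE count under this rule would not support a safety statement, and counts by arm would not be interpretable.

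This rests on two assumptions: that the study intervention means the FACE-Rare sessions, and that the relatedness clause governs the whole definition. It does not extend to a control family that takes up the intervention after its participation ends. If the Data Safety and Monitoring Plan already requires capture regardless of cause, the remaining task is to bring the protocol wording into line with it.

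**What to change.** Separate seriousness from relatedness.

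1. Take the attribution clause out of the SAE definition. Record every hospitalization or inpatient behavioral health stay for emotional distress in enrolled caregivers of both arms, from randomization to the 3-month visit.
2. Grade relatedness in its own field, with the SMC reviewing the PI's grading. State that grading does not delay the 24-hour report.
3. List events by arm, all-cause and related, without a test.
4. Reconcile the SAE definition and the SMC section on who receives the 24-hour report and when the clock starts. Correct the statement that the SAE definition rests on the Satisfaction Questionnaire.
5. Have the investigators and SMC restate, in the same amendment, which events trigger the study discontinuation. Removing the clause alone would tie that rule to any distress hospitalization, including a coincidental one in a control. Which events should trigger it is for them to decide.

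The cost is protocol wording, one field on the SAE form and one question at the 3-month visit. The downside is that a few unrelated events will be reported and the SAE count will look less favourable.
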